## 3 STUDY OBJECTIVES

### 3.1 Primary Objective

The primary objective of this study is to determine if azithromycin impairs the previously-recognized clinical benefits of inhaled tobramycin by comparing changes in pulmonary function as measured by FEV1 between subjects randomized to azithromycin versus placebo.

### 3.2 Secondary Objectives

The secondary objectives for the randomized period are to:

- Compare changes in patient-reported quality of life between subjects randomized to azithromycin versus placebo

The secondary exploratory objectives for the randomized period are to:

- Compare the safety profile between subjects randomized to azithromycin versus placebo.

- Compare changes in additional spirometry measures, bacterial density, and weight between subjects randomized to azithromycin versus placebo
- Compare rates of pulmonary exacerbations, hospitalizations, and acute antibiotic usage between subjects randomized to azithromycin versus placebo

The objectives for those continuing in the open-label extension:

- Among those randomized to azithromycin and remaining on azithromycin, obtain additional data to determine the long term effect of azithromycin on clinical outcomes
- Among those randomized to placebo and switching to azithromycin, compare differences in clinical outcomes observed during the randomized and open-label periods

## 4 STUDY DESIGN

### 4.1 Study Overview

This is a prospective, randomized, placebo-controlled, double-blinded study of azithromycin in subjects with chronic *Pa* airway infection using inhaled tobramycin. Subjects who have received two (2) or more cycles of inhaled tobramycin within the 24 weeks prior to enrollment will be recruited into the study. This study will investigate whether azithromycin is associated with poorer clinical and microbiologic outcomes as compared to placebo during concurrent administration of inhaled tobramycin.

[figure not shown]
Approximately 120 eligible subjects will be enrolled and randomized to either azithromycin or placebo at Visit 1, approximately 14 days prior to the start day of their next planned 28-day nebulized solution or dry powder tobramycin (TISP) cycle. Both tobramycin inhalation solution (TIS) and tobramycin inhalation powder (TIP) will be allowed, based on clinical prescription. Tobramycin solution should be nebulized with an approved nebulizer and air compressor.

Subjects will be randomized in a 1:1 fashion to azithromycin (500 mg three times per week) or matched placebo. Randomization will be stratified by FEV1 % predicted (25%-50%, >50%-75%, >75%), chronic oral azithromycin use for the past 30 days, inhaled tobramycin formulation (TIS or TIP), and site. Between Visit 1 (Day -14) and Visit 2 (Day 0), a two-week run-in period will be used to begin administration of either azithromycin or placebo. Among those randomized to azithromycin, the 2-week run-in period will be used to initiate azithromycin and standardize uptake prior to the start of the next TISP cycle. Among those randomized to placebo, the run-in period will be used as a standardized washout prior to the start of the next TISP cycle. Subjects will begin TISP at Visit 2 in addition to their continued dosing of randomized study drug treatment (azithromycin or placebo). Subjects will continue both TISP and study drug dosing for 28 days (up until Visit 3), which corresponds with the end of a clinically prescribed 4-week cycle of TISP.

Subjects completing the study through Visit 3 will be offered participation and consent to an 8-week open-label extension period during which azithromycin will be provided. During the open-label period, subjects will be instructed to remain off of TISP for the first 4-week period, followed by a 4-week period of TISP.

The total duration of the study is expected to be approximately 33.5 months: 30 months for subject recruitment and 3.5 months for the final subject enrolled to complete the study (Figure 7).

Figure 7. Study Schematic

A follow up safety visit is not necessary for this study as it does not expose subjects to new or investigational products.

## 5 CRITERIA FOR EVALUATION

### 5.1 Primary Endpoint

The primary endpoint in the study is the difference between the azithromycin and placebo treatment groups in the relative change in FEV1 (liters) from randomization (Visit 1) to Visit 3.

### 5.2 Secondary Endpoints

#### Randomized Period

Secondary Endpoints:

- Difference between the azithromycin and placebo treatment groups in the relative change in FEV1(liters) during administration of TISP from Visit 2 to Visit 3.
- Difference between the azithromycin and placebo treatment groups in the change from Visit 1 to Visit 3 in the Cystic Fibrosis Respiratory Symptom Diary (CFRSD) - Chronic Respiratory Infection Symptom Score (CRISS®)
- Difference between the azithromycin and placebo treatment groups in the change from Visit 1 to Visit 3 in the scales derived from the CFQ-R

Exploratory Secondary Endpoints:

- Difference in adverse event rates and rates of abnormal QTc parameters from Visit 1 through Visit 3 between the azithromycin and placebo treatment groups
- Difference in the proportion of subjects hospitalized from Visit 1 through Visit 3 between the azithromycin and placebo treatment groups
- Difference in the proportion of subjects

prescribed acute oral, inhaled and IV antibiotics from Visit 1 through Visit 3 between the azithromycin and placebo treatment groups

- Difference in the proportion of subjects experiencing a protocol-defined pulmonary exacerbation requiring antibiotic therapy from Visit 1 through Visit 3 between the azithromycin and placebo treatment groups
- Difference between the azithromycin and placebo treatment groups in the absolute change from Visit 1 to Visit 3 and Visit 2 to Visit 3 in FEV1 (liters and % predicted), absolute and relative change in FVC (liters and % predicted), and absolute and relative change in FEF25-75%
- Difference between the azithromycin and placebo treatment groups in the change from Visit 1 to Visit 3 in weight
- Difference in the change from Visit 1 to Visit 3 in sputum *Pa* bacterial density between the azithromycin and placebo treatment groups

### Open-Label Period

- Among those randomized to azithromycin and remaining on azithromycin, longitudinal changes and/or rates in all clinical outcomes across the randomized and open-label periods
- Among those randomized to placebo and switching to azithromycin, differences in all clinical outcomes between the randomized and open-label periods

## 6 SUBJECT SELECTION

### 6.1 Study Population

Subjects with a diagnosis of CF who meet all of the inclusion and none of the exclusion criteria will be eligible for enrollment in this study.

### 6.2 Inclusion Criteria

#### Inclusion Criteria for Randomized Period:

1. Male or female  $\geq 12$  years of age at Visit 1
2. Documentation of a CF diagnosis as evidenced by one or more clinical features consistent with the CF phenotype and one or more of the following criteria:
  - Sweat chloride equal to or greater than 60 mEq/L by quantitative pilocarpine iontophoresis test (QPIT)
  - Two mutations in the CFTR gene believed to be disease causing in the opinion of the site investigator
  - Abnormal nasal potential difference (change in NPD in response to a low chloride solution and isoproterenol of less polarizing than -7 mV)
3. Written informed consent (and assent when applicable) obtained from subject or subject's legal representative
4. Two or more respiratory cultures (sputum, OP swab, BAL sample) growing *Pa* collected within the 12 months prior to randomization, at least 1 month apart, with at least one collected in the 6 months prior to randomization
5. FEV1% predicted between 25-100% at Visit 1

6. Off TISP and other inhaled anti-pseudomonal antibiotics for at least two weeks at randomization
7. Willingness to begin the next course of TISP at the scheduled Visit 2
8. Use of at least 2 cycles of TISP within 24 weeks prior to Visit 1
9. Ability to swallow capsules (similar in size to pancreatic enzyme capsules)
10. Most recent LFTs less than 4x ULN. Must be obtained within 12 months prior to Visit 1
11. Current azithromycin use at Visit 1 or prior chronic azithromycin use defined as four or more consecutive weeks. Subjects do not have to be using chronic oral azithromycin at Visit 1
12. Stable clinical status with no significant change in medication or airway clearance routine for four weeks prior to Visit 1, as determined by site investigator

Inclusion Criteria for Open-Label Period:

1. Completion of the randomized, placebo-controlled period (up through Visit 3)
2. Written informed consent (and assent when applicable) obtained from subject or subject's legal representative
3. Ability for subject to comply with the requirements of the study
4. Willingness to begin the next course of TISP at the scheduled Visit 4
5. Clinically stable at Visit 3 as assessed by the site investigator

### **6.3 Exclusion Criteria**

Exclusion Criteria for Randomized Period:

1. Weight < 40 kg at Visit 1
2. For women of child-bearing potential:
  - a. positive pregnancy test at Visit 1 or
  - b. lactating or
  - c. unwilling to practice a medically acceptable form of contraception (acceptable forms of contraception: abstinence, hormonal birth control, intrauterine device, or barrier method plus a spermicidal agent), unless surgically sterilized or postmenopausal during the study
3. Inability to perform reproducible spirometry
4. Inability or unwillingness to cycle off TISP for one 4-week period
5. Respiratory culture with *Burkholderia cepacia* complex species within the 24 months prior to Visit 1
6. Respiratory culture with nontuberculous mycobacteria (NTM) within 18 months prior to Visit 1
7. Use of IV or oral anti-pseudomonal antibiotics within four weeks prior to Visit 1 (other than azithromycin)
8. Use of an investigational therapy within four weeks prior to Visit 1
9. History of unresolved, abnormal neutropenia ( $ANC \leq 1000$  cells/mm^3)
10. Current use of systemic corticosteroids equivalent to a daily dose more than 10 mg prednisone at Visit 1

11. Current use of nelfinavir, warfarin, haloperidol, or methadone at Visit 1
12. Initiation of approved CFTR modulators less than 30 days prior to Visit 1
13. ECG abnormalities identified at Visit 1 that require prompt, further medical evaluation or QTc interval >480 msec for males and >486 msec for females at Visit 1
14. Any other condition that, in the opinion of the site investigator/designee, would preclude informed consent or assent, make study participation unsafe, complicate interpretation of study outcome data, or otherwise interfere with achieving the study objectives

#### Exclusion Criteria for Open-Label Period:

1. Weight < 40 kg at Visit 3
2. For women of child bearing potential: unwilling to practice a medically acceptable form of contraception (acceptable forms of contraception: abstinence, hormonal birth control, intrauterine device, or barrier method plus a spermicidal agent), unless surgically sterilized or postmenopausal during the study
3. Identified respiratory culture positive for NTM or *Burkholderia cepacia* complex species during randomized study period
4. Use of an investigational therapy at Visit 3
5. Current use of systemic corticosteroids equivalent to a daily dose more than 10 mg prednisone
6. Current use of nelfinavir, warfarin, haloperidol, or methadone
7. Any other condition that, in the opinion of the site investigator/designee, would preclude informed consent or assent, make study participation unsafe, complicate interpretation of study outcome data, or otherwise interfere with achieving the study objectives

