## 9.2 Clinical Laboratory Measurements

### 9.2.1 Pregnancy Test

Urine or blood (approximately 2 cc) will be collected from females who are of childbearing potential for a pregnancy test as noted in the Schedule of Events and tested by the site according to site standard procedures.

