## 10 EVALUATIONS BY VISIT

### Randomized Period

#### 10.1 Visit 1 – Day -14

\*A respiratory culture may be obtained prior to randomization to confirm eligibility criteria #4. If a respiratory culture is needed, the remaining Visit 1 procedures should be completed after confirming positive *Pa* culture results.

1. Review the study with the subject (subject's legal representative) and obtain written informed consent and HIPAA authorization and assent, if appropriate.
2. Assign the subject a unique study number.
3. If there is not a recent respiratory culture available, obtain culture to confirm eligibility:
  - Review culture results.
  - If *Pa* positive and meets criteria #4, schedule subsequent visit to complete remaining Visit 1 procedures.
  - If *Pa* negative, record as Screen Fail.
4. Review and record previous use of azithromycin and inhaled tobramycin.
5. Record demographics and CFF Registry ID, if consent obtained.
6. Record medical history, including a history of CF diagnosis and date.
7. Record concomitant medications.
8. Administer PRO questionnaires (CFRSD-CRISS and CFQ-R).
9. Perform a complete physical examination.
10. Measure and record height and weight.
11. Obtain and record vital signs.

12. Perform and record spirometry.
13. Collect blood or urine for pregnancy test (if female of child-bearing potential).
14. Obtain resting ECG.
15. If able to expectorate sputum, collect expectorated sputum.
16. Confirm subject eligibility.
17. Randomize to study drug.
18. Dispense study drug.
19. Review study drug dose and schedule with subject.
20. Provide subject diary and instructions for completion.
21. Remind subject to NOT use inhaled tobramycin between this day and Visit 2.
22. Instruct subject to bring study drug bottle, any remaining capsules, and diary to Visit 2.
23. Schedule subject for Visit 2.

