### Visit 3: Additional procedures for subjects enrolling in the open-label extension

13. Assess subject eligibility for open-label extension
14. Review the open-label extension period of the study with the subject (subject's legal representative) and obtain written informed consent and HIPAA authorization and assent, if appropriate.
15. Dispense open-label azithromycin.
16. Provide subject diary.
17. Remind subject to NOT use inhaled tobramycin between this day and Visit 4.
18. Instruct to bring the azithromycin bottle, any remaining tablets, and diary to Visit 4.
19. Schedule subject for Visit 4.

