## 12 DISCONTINUATION AND REPLACEMENT OF SUBJECTS

### 12.1 Early Permanent Discontinuation of Study Treatment

A subject may be permanently discontinued from study treatment at any time if the subject, the investigator, or the Sponsor-Investigator feels that it is not in the subject's best interest to continue. The following is a list of possible reasons for early permanent discontinuation of study treatment:

- Subject or subject's legal representative decision
- Adverse event, including pulmonary exacerbation
- Protocol violation
- Death

If a subject is discontinued from treatment due to an AE, the subject will be followed and treated by the site investigator until the abnormal parameter or symptom has resolved or stabilized.

All subjects who permanently discontinue study treatment early should come in for an early discontinuation of study treatment visit as soon as possible (see Appendix 1) and then should be encouraged to complete all remaining scheduled visits and procedures.

Refer to Section 8.6.2 for temporary discontinuation of study drug.

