## 19 APPENDIX 1 SCHEDULE OF EVENTS

	RANDOMIZED, PLACEBO-CONTROLLED, DOUBLE BLIND		OVERLAP	OPEN-LABEL, FOLLOW-ON		UNSCHEDULED/ EARLY TERM VISIT f
	VISIT 1* Day -14	VISIT 2 (Day 0) (-2 to +4 days)	VISIT 3 Day 28 (-2 to +4 days)	VISIT 4 EXT Day 56 (± 4 days)	VISIT 5 EXT Day 84 (±4 days)	
Informed Consent	X		X e			
Respiratory Culture (as needed)	X h					
Demographics and Medical History	X					
Complete CFQ-R and CFRSD-CRISS	X	X	X	X	X	X
Complete Physical Exam	X					X
Abbreviated Physical Exam		X	X	X	X	
Height	X	X	X	X	X	X
Weight	X	X	X	X	X	X
Vital Signs	X	X	X	X	X	X
Spirometry	X	X	X	X	X	X
Pregnancy Test at site (Urine or Serum) a	X					
ECG Testing	X		X		X	X b
Collect sputum for analysis and banking c	X	X	X	X	X	X
Randomize to azithromycin or placebo	X					
Dispense azithromycin/placebo dose and review dose schedule	X					
Dispense open-label azithromycin and review dose schedule			X e			
Provide Subject Diary	X	X	X e	X		

	RANDOMIZED, PLACEBO-CONTROLLED, DOUBLE BLIND		OVERLAP	OPEN-LABEL, FOLLOW-ON		UNSCHEDULED/ EARLY TERM VISIT f
	VISIT 1* Day -14	VISIT 2 (Day 0) (-2 to +4 days)	VISIT 3 Day 28 (-2 to +4 days)	VISIT 4 EXT Day 56 (± 4 days)	VISIT 5 EXT Day 84 (±4 days)	
Instruct to hold use of inhaled tobramycin for off-cycle until the next study visit	X		X e			
Concomitant Medication Review	X	X	X	X	X	X
Adverse Events		X	X	X	X	X
Review Subject Diary and pill count		X	X	X	X	X
Record TISP use			X		X	X
Review inhaled tobramycin schedule		X		X		
Assess eligibility for Open-label			X e			
Signs and Symptoms Assessment g	Start	➔	Stop Start e	➔	Stop	

\* If the patient does not have sufficient culture history to assess eligibility, a respiratory culture may be collected prior to randomization. If the respiratory culture is positive, the remaining Visit 1 procedures and randomization will be conducted at a subsequent visit.

a Only females of child-bearing potential

b ECG is only required at an Unscheduled visit (if the subject has a cardiovascular related adverse event) or at an Early Termination Visit (when the subject permanently discontinues study drug or will no longer be participating in the study)

c Expecterated sputum will be collected from subjects who are able to produce sputum

e Perform only if rolling over into Open-Label

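### The open-label exclusions drop the pregnancy and lactation items applied at Visit 1, and no repeat pregnancy test is scheduled before azithromycin is dispensed at Visit 3

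*Protocol*

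**What the plan says.** **Entry to the randomized period (Protocol 6.3 and synopsis).** Exclusion 2 has three limbs for women of child-bearing potential. Limb 2a reads "positive pregnancy test at Visit 1 or", limb 2b is lactation, and limb 2c is unwillingness to use contraception. Exclusion 14 is a general investigator-judgement criterion that stands in addition to these.

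**Entry to the open-label period (Protocol 6.3 and synopsis).** Exclusion 2 contains one limb: "For women of child bearing potential: unwilling to practice a medically acceptable form of contraception". Neither pregnancy nor lactation is named. Exclusion 7 is the same kind of general criterion as exclusion 14, and open-label inclusion 5 asks the investigator to judge clinical stability at Visit 3.

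**Testing.** Section 9.2.1 has urine or blood collected from "females who are of childbearing potential for a pregnancy test as noted in the Schedule of Events". The schedule in Appendix 1 marks the test at Visit 1 only. The visit lists agree: the test is step 13 in 10.1 and does not appear in 10.2 to 10.6.

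**Dispensing.** The additional Visit 3 procedures for subjects who roll over include an eligibility check (step 13), new consent (step 14) and then "Dispense open-label azithromycin" (step 15).

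**The concern.** At first entry the protocol did not leave pregnancy to the general judgement criterion; it named the condition and tested for it. Pregnancy status can change over six weeks, and the open-label list re-checks other things that can change: weight, steroid dose, the four named prohibited drugs, investigational therapy and respiratory cultures. The ECG is also repeated at Visit 3. Pregnancy is not re-checked.

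A woman who becomes pregnant during the randomized period therefore meets no named open-label exclusion. If she knows she is pregnant, the investigator can decline her. If she does not, nothing in the Visit 3 procedures would reveal it, and she is given eight weeks of azithromycin by the trial. For women randomized to placebo this is the trial starting azithromycin, not continuing it.

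This is a matter of participant safety and of consistency between two eligibility lists. It is not a matter of inference: the primary endpoint runs from Visit 1 to Visit 3 and is complete when the open-label drug is dispensed.

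**Working it through.** The plan states no figure on this point, so there is none to reproduce. The check has three parts.

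**1. The two lists side by side**

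| Item for women of child-bearing potential | Randomized exclusion 2 | Open-label exclusion 2 |
|---|---|---|
| Positive pregnancy test | Yes (2a, at Visit 1) | No |
| Lactating | Yes (2b) | No |
| Unwilling to use contraception | Yes (2c) | Yes |
| General judgement criterion elsewhere in the list | Yes (14) | Yes (7) |
| Pregnancy test among that visit's procedures | Yes (10.1, step 13) | No (10.3, steps 1 to 19) |

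The synopsis, 6.3, the visit lists and Appendix 1 all agree, so the gap is not an error in one table.

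**2. Age of the only scheduled test at dispensing**

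Inputs: Visit 1 is Day -14 and Visit 3 is Day 28 with a window of -2/+4 days (10.1, 10.3). The synopsis gives the two treatment periods as 14 days and 28 days, each -2/+4.

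- Nominal: 14 + 28 = 42 days.
- Window read around Day 28 only: 26 + 14 = 40 to 32 + 14 = 46 days.
- Period windows added: 12 + 26 = 38 to 18 + 32 = 50 days.

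The same test then stands for a nominal further 28 + 28 = 56 days of open-label treatment, 98 days in all.

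**3. How many women might be affected**

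The documents give neither the number of women of child-bearing potential, nor the roll-over rate, nor a pregnancy rate. For scale only, assume n = 30 to 60 such women roll over and a yearly pregnancy probability r = 1% to 10% on an accepted method. Expected new pregnancies over d days = n × (1 − (1 − r)^(d/365)).

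| n | r | d (days) | Expected |
|---|---|---|---|
| 30 | 0.01 | 38 | 0.031 |
| 30 | 0.01 | 42 | 0.035 |
| 60 | 0.05 | 42 | 0.353 |
| 60 | 0.10 | 42 | 0.723 |
| 60 | 0.10 | 50 | 0.860 |

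The range is 0.03 to 0.72 at the nominal interval and 0.03 to 0.86 over 38 to 50 days. It counts every new pregnancy, including those the woman already knows about and the investigator could act on, so it overstates what an added test would catch. The upper end is also generous: n = 60 would be half of the 120 subjects randomized.

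**The case against.** The case for leaving the protocol as it stands has some force.

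- **Familiar drug.** Inclusion 11 requires "Current azithromycin use at Visit 1 or prior chronic azithromycin use defined as four or more consecutive weeks", so every subject has taken azithromycin before. Section 2.1 says no new or experimental drug is introduced, and the open-label supply is a commercial product. For women in the azithromycin arm, Visit 3 continues an exposure they already have. This limits the concern but does not remove it. All of it was equally true at Visit 1, where pregnancy was still named and tested. Inclusion 11 also admits women not taking azithromycin at entry. Section 4.1 uses the absence of new products to justify having no safety follow-up visit, not to justify omitting a pregnancy check.
- **Existing safeguards.** Contraception is required at entry and assessed again at Visit 3, fresh consent is taken, and open-label exclusion 7 can be used for a known pregnancy. The consent forms, which are not part of the protocol text or SAP, may contain pregnancy instructions and cannot be assumed silent. What remains is a pregnancy that occurs despite contraception and is not yet recognised.
- **A deliberately shorter list.** The open-label list also omits randomized-period exclusions 3, 4, 7, 9, 12 and 13, so pregnancy was not singled out. That explains the omission, but it gives no reason for keeping one limb of a three-limb criterion and losing two.

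A reader might infer more than the documents support:

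- *That no pregnancy test precedes open-label dosing at all.* One does, at Visit 1. Only the repeat is missing.
- *That pregnancy is no ground for stopping treatment, because 12.1 does not list it.* That list is introduced with "The following is a list of possible reasons for early permanent discontinuation of study treatment", and the section lets treatment be stopped whenever continuing is not in the subject's interest.
- *That a subject stopped for intolerance (8.6.1) or a confirmed QTc abnormality (9.1.13) could freely restart in the open-label period.* Most of the text points the other way. SAP 2.5 counts open-label azithromycin as study drug, 9.1.13 applies its stop to both, and exclusion 7 is available. No extra exclusion line is needed on this account.

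**Conclusion.** The gap is confirmed. Open-label exclusion 2 drops both the pregnancy and the lactation limbs, and no test is repeated in the nominal 42 days (38 to 50) between Visit 1 and open-label dispensing. The judgement criteria cannot catch a pregnancy that nobody knows about.

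The point is minor. Under the stated assumptions fewer than one woman in the trial would be affected, and those assumptions are for scale only because the documents supply none of the inputs. The documents also give no figure for the risk of azithromycin in pregnancy, so the harm per case cannot be sized from them. The lactation limb matters mainly for consistency: a woman who was neither pregnant nor lactating at Visit 1 is very unlikely to be lactating six weeks later. Power, type I error and the randomized comparison are untouched. The reason to act is that the protocol's own entry standard is not carried over and that restoring it costs very little.

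**What to change.** - In 6.3 and the synopsis, extend open-label exclusion 2 with: *pregnant (positive test or known pregnancy) or lactating at Visit 3*.
- In 10.3, add a urine pregnancy test to the additional procedures for women of child-bearing potential who roll over, placed before the dispensing step.
- In Appendix 1, mark the pregnancy test at Visit 3 under footnote e (roll-over subjects only). Section 9.2.1 then needs no change, because it already defers to the schedule.

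The cost is one wording change in two places, one procedure step, one table entry and one urine test per woman of child-bearing potential who rolls over, using a procedure sites already perform at Visit 1. The downside is possibly slightly fewer subjects, and so slightly less data, in an optional extension. Nothing in the randomized period changes.
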